3.1.5 Missing data

Missing data will not be imputed except for the following:

QMG and MGC are allowed to have partially completed assessments per the system setup. If $\leq 50\%$ of the individual items in the questionnaire are missing at a visit, the missing items will be imputed using last observation carried forward (LOCF) before the calculation of the total scores. If $> 50\%$ of the individual items are missing, the total score at that visit will be considered as missing and no imputation will be applied. For the other questionnaires, the individual items in the questionnaire will be either all available or all missing per the system setup. No imputation will be applied to these missing records.

3.2 Protocol Deviations

All protocol deviations (PD) will be reviewed, documented, and classified as critical PDs, major PDs, or minor PDs prior to the database lock according to the PD guidelines.

All critical and major PDs will be summarized.

3.3 Study Subjects

3.3.1 Subject Disposition

Subject disposition will be summarized using all the subjects enrolled into the study. The total number of subjects will be summarized for those who were enrolled, who were screen failed, and who were randomized. The numbers and the percentages of the subjects will be summarized for the following groups in the overall study, AChR-Ab+ and MuSK-Ab+ population, respectively.

- Subjects who are randomized

- Subjects who discontinued treatment during the RCP
- Subjects who early discontinued **participation** from the RCP
- Subjects who completed RCP
- Subjects who entered OLP
- Subjects who discontinued treatment during the OLP
- Subjects who early discontinued from the OLP
- Subjects who entered SFP

3.3.2 Demographics, Baseline Characteristics, and Medical History

Demographic data and key baseline characteristics will be summarized using descriptive statistics on FAS. The demographic data and key baseline characteristics will include but are not limited to the following variables.

- Demographic: age, gender, race, ethnicity, height, weight, and body mass index.
- Baseline Characteristics: baseline antibody status, MG-ADL score, QMG score, MGFA class, MGC Score, PGIC, MGQOL-15r score, Steroid use, non-steroid IST use and CD20+ B-cell count etc.

Significant medical history findings will be summarized by MedDRA system organ class (SOC) and preferred term (PT).

3.3.3 Study Drug Exposure

The total number of doses received, total amount of inebilizumab received, total duration of the inebilizumab exposure, and treatment compliance will be summarized within RCP, OLP, and Combined RCP and OLP, respectively.

- Total duration of the inebilizumab exposure (days) = last inebilizumab dose date in a specific study period – first inebilizumab dose date within that study period [REDACTED]
- The amount of inebilizumab exposure at each visit: if a subject received partial dose at a dosing visit, then the amount of inebilizumab at that dosing visit will be estimated based on the actual volume administered. and the dose administered = intended dose (300 mg) x x actual volume received/planned volume. If a subject received placebo at a dosing visit, then the amount of inebilizumab at that visit is 0 mg.
- Treatment compliance for an individual subject = [Total number of IP doses received during a specific study period] / [Total number of IP doses planned per protocol within that study period] x x100%.

3.3.4 Concomitant Medications

Number (%) of subjects who received concomitant medications (coded according to WHO Drug dictionary) will be summarized within RCP and OLP, respectively, as appropriate. At each level of summarization, a subject is counted once if the subject reported one or more medications at that level. The concomitant medications are defined as below. In addition, separate analyses of steroid usage for MG disease control and analyses of the rescue therapy usage for MG crisis will be conducted.

- Concomitant medications for RCP are defined as:
 - 1) Medications started between the first RCP IP dose date and the end of the RCP (inclusive), or
 - 2) Medications stopped between the first RCP IP dose date and the end of the RCP (inclusive), or
 - 3) Medications started before the first RCP IP dose date, and ongoing before the end of the RCP.
- Concomitant medications for OLP are defined as:
 - 1) Medications started on or after the first OLP IP dose, or
 - 2) Medications stopped on or after the first OLP IP dose, or
 - 3) Medications started before the first OLP IP dose and did not stop during OLP.

Missing start/stop dates will be imputed as appropriate, and the details of the imputation will be included in the SPP.

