### 6.1.3 Open-label Period

Subjects who complete the RCP have the option to enroll in the OLP study. Subjects who discontinue the RCP early are not eligible to enter the OLP. Informed consent for OLP participation must be obtained at the time of OLP entry.

The study OLP duration is 3 years for both study populations, AChR+ and MuSK+. The OLP assessments are the same for both study populations.

Upon completing all the assessments at the last RCP visit, it is strongly recommended to perform the OLP Day 1 visit on the same day. The OLP Day 1 visit may occur for up to 14 days after the final RCP visit. Many assessments are common to both the final RCP visit and OLP Day 1 visit and do not need to be repeated if done within 14 days of the final RCP visit (see [Table 5](#), footnote b). Subjects are not permitted to enter the OLP after 14 days after the final RCP visit without the Sponsor's written approval.

During the OLP, subjects' treatment assignment will remain blinded. The OLP will include IP infusions on OLP Days 1, 15, and 183, and every 6 months thereafter at Days 365, 547, 729, and 911. All subjects will receive inebilizumab on OLP Days 1, 183, 365, 547, 729, and 911. On OLP Day 15, subjects who received inebilizumab in the RCP will receive placebo and subjects who received placebo in the RCP will receive inebilizumab. This will allow subjects who are just beginning inebilizumab to receive the full 2-dose initial treatment course while maintaining blinding of the RCP treatment assignment.

For more details about OLP assessments, see [Table 5](#).

Subjects will continue to be followed for an additional 26 weeks after the last dose of inebilizumab (at OLP Day 911) until OLP Day 1093.

It is recommended to taper non-steroidal ISTs (eg, azathioprine, mycophenolate mofetil, mycophenolic acid) per standard of care. For subjects on tacrolimus (allowed in Japan only), taper of tacrolimus is recommended. The rationale for tapering non-steroidal ISTs in the OLP is to reduce potential risks associated with long-term use of multiple ISTs.

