- Receipt of medications that target B cells or immunoglobulins during the SFUP requires immediate withdrawal from the SFUP. This includes any immunomodulatory or immunosuppressive drugs which have a pharmacodynamic effect on B cells and/or immunoglobulins (eg, rituximab, ocrelizumab, ofatumumab, obinutuzumab, or any experimental B cell depleting or modulating agent).
- Receipt of other protocol-defined prohibited medications (Section [7.5.1](#)), such as azathioprine or mycophenolate mofetil during the SFUP must be discussed with the Sponsor to determine whether the subject may continue participation in the SFUP.

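### Read as written, the SAP's definition of concomitant medication in the open-label period has no effective date limit, so the OLP table could include drugs stopped before that period or first taken after it

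*SAP*

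**What the plan says.** SAP 3.3.4 (Concomitant Medications) plans a count and percentage of subjects by medication, which "will be summarized within RCP and OLP, respectively, as appropriate". A subject counts once at each level of the table. A medication belongs to the OLP if any one of three conditions holds:

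- Condition 1 looks only at when the drug began: "Medications started on or after the first OLP IP dose, or"
- Condition 2 puts the same open-ended test on the stop date, with no limit at the close of the period.
- Condition 3 covers drugs begun earlier: "Medications started before the first OLP IP dose and did not stop during OLP"

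The RCP definition just above it is closed at both ends. Its first condition reads "Medications started between the first RCP IP dose date and the end of the RCP (inclusive), or", its second puts the same limits on the stop date, and its third asks for a drug begun earlier and still ongoing.

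The same section adds that "separate analyses of steroid usage for MG disease control and analyses of the rescue therapy usage for MG crisis will be conducted", and leaves the imputation of missing dates to the statistical programming plan (SPP). It defines no category for prior medication or for medication taken in the safety follow-up.

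**The concern.** The table is meant to show what subjects took during the OLP, yet none of the three conditions restricts it to that period. Condition 3 does not require the drug to be in use when the OLP starts. Conditions 1 and 2 do not require anything to have happened before the OLP ends.

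At stake is an accurate description of background treatment in the OLP. On immunosuppressive therapies (ISTs) in that period, Protocol 6.1.3 says "It is recommended to taper non-steroidal ISTs", so a reader will want to know which ISTs were actually taken then. A B-cell agent started in follow-up but listed under the OLP would wrongly suggest use in the OLP alongside inebilizumab.

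**Working it through.** The plan gives no figure to reproduce. The check is logical.

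**Notation.** S is the start date and E the stop date (blank if ongoing). A is the first OLP dose and B the end of the OLP.

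- Condition 1: S ≥ A
- Condition 2: E ≥ A
- Condition 3: S < A, and E does not fall between A and B
- True OLP use: S ≤ B, and E is blank or E ≥ A

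**Do the conditions exclude anything?** If S ≥ A, condition 1 holds. If S < A, either E lies between A and B, so condition 2 holds, or it does not, so condition 3 holds. Every dated record of a subject with a first OLP dose is therefore admitted.

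**Every pattern by period.** Starts can fall before the RCP, in the RCP, in the OLP or in the safety follow-up. Stops can fall in the same or a later period, or the drug can be ongoing: 5 + 4 + 3 + 2 = 14 patterns.

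| Start | Stop | Admitted by condition | Taken in OLP? |
|---|---|---|---|
| Before RCP | Before RCP | 3 | **No** |
| Before RCP | RCP | 3 | **No** |
| Before RCP | OLP | 2 | Yes |
| Before RCP | Follow-up | 2, 3 | Yes |
| Before RCP | Ongoing | 3 | Yes |
| RCP | RCP | 3 | **No** |
| RCP | OLP | 2 | Yes |
| RCP | Follow-up | 2, 3 | Yes |
| RCP | Ongoing | 3 | Yes |
| OLP | OLP | 1, 2 | Yes |
| OLP | Follow-up | 1, 2 | Yes |
| OLP | Ongoing | 1 | Yes |
| Follow-up | Follow-up | 1, 2 | **No** |
| Follow-up | Ongoing | 1 | **No** |

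All 14 are admitted and 9 overlap the OLP, so 14 − 9 = 5 are wrongly included: three through condition 3, and two through condition 1 (one of these also through condition 2). No true OLP use is missed, so literal coding can only raise the counts.

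**Can such records exist?** Yes.

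- Protocol Table 6 collects concomitant medications in follow-up.
- Protocol 7.5.2 foresees azathioprine or mycophenolate mofetil being taken in follow-up, subject to discussion with the sponsor.
- Of B-cell agents the same section says "Receipt of medications that target B cells or immunoglobulins during the SFUP requires immediate withdrawal from the SFUP". A record of the drug that triggers withdrawal would still meet condition 1.
- Protocol 6.2.2 records earlier chronic immunosuppressants.
- For a subject who completes the OLP, the last dose is on Day 911 and the OLP ends on Day 1093 (Protocol 6.1.3). Follow-up lasts up to 730 days after the last dose (Protocol Synopsis). 911 + 730 = 1641, and 1641 − 1093 = 548 days, about 1.5 years beyond the OLP. It is shorter if B-cell recovery ends follow-up sooner.

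**The overlap rule.** Requiring S ≤ B, and E blank or E ≥ A, admits the 9 true patterns and none of the 5 others.

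**The case against.** The best defence is that the intent is plain. The section says the summary is within each period. Condition 2 already takes drugs stopped after OLP entry, so condition 3 is naturally its complement, drugs still ongoing, as in the RCP rule. A sensible programmer would code it so, and the SPP, which is not available, may do just that.

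For condition 3 this has force: the error depends on literal coding. For conditions 1 and 2 it has less, because nothing in the definition supplies the missing end date and the section cites the SPP only for date imputation.

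The limits on the effect also stand. A subject's count changes only if all of that subject's use at a given level lay outside the OLP. Under Protocol 4.1 and 7.5.2, non-steroidal ISTs normally continue through the RCP, and prednisone above 5 mg/day is tapered to 5 mg/day and held there to the end of the RCP. Such subjects would usually enter the OLP still on the drug and be counted correctly.

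A reader might infer more than the documents support:

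- **That OLP immunosuppressant and steroid use is overstated.** Only that it could be. The steroid part is weakest: steroid use for MG has its own analysis, and corticosteroid premedication precedes each inebilizumab infusion (Protocol 7.1.1.4). If that is recorded as concomitant medication, which is an assumption, nearly every OLP subject is already in the corticosteroid class.
- **That the table hides successful IST withdrawal.** A subject who tapers off during the OLP is a true OLP user under either rule. A once-per-subject count cannot show withdrawal.
- **That conclusions on durability or infection are affected.** No visible analysis takes this table as input. SAP 3.1 addresses durability by summarizing efficacy over the combined RCP and OLP, and SAP 3.5.2 relates infections to immunoglobulin levels.
- **That the RCP rule has the same fault.** No defect is shown there. Its first two conditions are bounded and its third asks for ongoing use.

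**Conclusion.** The point holds as a defect in a stated rule. Applied as written, the OLP definition admits every dated medication record of a subject with a first OLP dose, including 5 of 14 patterns with no use in the OLP. The missing upper bound in conditions 1 and 2 is the firmer gap; condition 3 is loosely worded.

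The consequence is conditional on literal programming, and any error is upward. It would fall mainly on drugs stopped before OLP entry and on drugs first taken in follow-up. The 5 of 14 counts patterns, not subjects, and the documents hold no medication data from which to size the effect. The table is descriptive: no tested endpoint, estimand or multiplicity step depends on it. This is a minor correction worth making because it is so cheap.

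**What to change.** In SAP 3.3.4, replace the three OLP conditions with one overlap rule: a medication is concomitant for the OLP if its start date is on or before the end of the OLP and its stop date is on or after the first OLP dose, or it is ongoing.

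Equivalently, keep the three conditions, bound both 1 and 2 at the end of the OLP, and reword 3 to require that the drug began before the first OLP dose and was still in use at that dose. Both bounds are needed: with only condition 1 closed, a drug started and stopped in follow-up would still enter through condition 2. State the end of the OLP as a date for each subject, for example the Day 1093 or early discontinuation visit in Protocol Table 5.

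The cost is one sentence in the SAP and matching code. Data collection and the tested analyses are unaffected, and the RCP rule needs no change.

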3.4 Analyses Methods

3.4.1 Intercurrent events and Strategies

Potential intercurrent events such as discontinuing from the treatment, early discontinuing from the study, death, or initiating rescue therapy, which includes intravenous immunoglobulin (IVIg) or plasma exchange (PLEX), may occur during the study. Subjects who discontinue from the treatment and/or receive rescue therapy will be encouraged to stay in the study after those intercurrent events and data will be collected through planned study completion. These intercurrent events will be addressed using different strategies in the efficacy and safety analyses as appropriate. The following analyses strategies will be used and detailed components of each strategy are included in the sub-sections under Section 3.4 and Section 3.5.

Treatment-policy strategy: The analyses will include all data captured in each study period, defined as the period after randomization to the conclusion of the last scheduled visit in the corresponding study period regardless of the rescue therapy use.

While on-treatment strategy: The analyses will include all data captured while subjects are on treatment during the RCP, [REDACTED]

All efficacy analyses described below apply to the RCP unless stated otherwise. The efficacy endpoints will be analyzed in the overall study population, AChR-Ab+ population, and MuSK-Ab + population, respectively, [REDACTED] as suitable. Supplementary analyses using treatment-policy strategy will be conducted for primary endpoint and key secondary endpoints to assess the robustness of the conclusions. For subjects in the OLP, the efficacy may also be summarized based on OLP and the combined RCP and OLP using treatment-policy strategy, if applicable.

The safety endpoints will be summarized for the RCP, OLP, **and combined RCP and OLP** separately and analyzed using treatment-policy strategy. Summary of AEs/ SAEs/ AESIs, CD20+ B-cell count, and Serum Immunoglobulins would be provided for subjects based on combined RCP and OLP, and based on SFP if applicable.. [REDACTED] may be conducted using while on-treatment strategy for TEAE/TESAE/AESI as needed.

3.4.2 Primary Efficacy Endpoint and Analyses

[figure not shown]
3.4.2.1 Primary Efficacy Endpoint

The primary efficacy endpoint is the change from baseline in MG-ADL score at Week 26 in the overall study population (AChR-Ab+ and MuSK-Ab+). The primary analysis will be conducted after all subjects complete the Week 26 visit or end of study visit if the subject discontinues from the study before the Week 26 visit.

3.4.2.2 Analyses for Primary Efficacy Endpoint

For the primary analysis, the primary estimand is defined as follows:

1. Population: Subjects in the FAS.
2. Variable (endpoint): change from baseline in MG-ADL score at Week 26.
3. Intercurrent events:

4. Population-level summary: Mean difference between inebilizumab and placebo.

Rationale for estimand: The occurrence of the intercurrent event of rescue therapy is informative about the effect of treatment. If a subject is administered rescue therapy after Day 28, it may be considered that the allocated treatment was not effective, and the subject was not successfully treated. Taking rescue therapy will confound treatment effect.

[figure not shown]
The primary endpoint will be analyzed using a mixed-effects model for repeated measures (MMRM) analysis [REDACTED]

[figure not shown]
[REDACTED] The estimate of the treatment effect estimator will be based on a contrast from this MMRM model. The variance-covariance

matrix will be assumed to be unstructured. If the procedure doesn't converge, then a compound symmetric variance-covariance matrix will be applied.

Supplementary analysis will be performed for the primary efficacy endpoint using a treatment-policy strategy to address both intercurrent events of rescue therapy and treatment discontinuation (i.e., including data collected after rescue therapy and treatment discontinuation in the analysis).

The primary analysis will be conducted using the MMRM, which is valid under the missing at random (MAR) assumption. To examine the sensitivity of the results of the primary analysis to departures from the underlying MAR assumptions, additional analyses using Partial Dropout Reason-based Multiple Imputation (Partial-DRMI) and Dropout Reason-based Multiple Imputation (DRMI) will be performed as mentioned in Section 3.4.2.3.

3.4.3 Key Secondary Efficacy Endpoints and Analyses

3.4.3.1 Key Secondary Efficacy Endpoints

The key secondary efficacy endpoints are as follows:

CONFIDENTIAL AND
PROPRIETARY

[figure not shown]
- Change from baseline in QMG scores at Week 26 in the overall study population.
- Change from baseline in MG-ADL score at Week 26 in the AChR-Ab+ population.
- Change from baseline in QMG score at Week 26 in the AChR-Ab+ population.
- Change from baseline in MG-ADL score at Week 26 in the MuSK-Ab+ population.
- Change from baseline in QMG score at Week 26 in the MuSK-Ab+ population.

3.4.3.2 Key Secondary Efficacy Analyses

[figure not shown]
Change from baseline in QMG scores at Week 26 in the overall study population

The primary estimand of the changes from baseline in QMG score in the overall study population at Week 26 is defined as follows:

[figure not shown]
- Population: Subjects in the FAS.
- Variable (endpoint): Change from baseline at Week 26.
- Intercurrent event:

- Population-level summary: Mean difference between inebilizumab and placebo.

The estimate of the treatment effect estimator will be based on a contrast from a MMRM model

[REDACTED]

Changes from baseline in MG-ADL at Week 26 in the AChR-Ab+ population and Changes from baseline in MG-ADL at Week 26 in the MuSK-Ab+ population

The definitions of primary estimand of the changes from baseline in MG-ADL score at Week 26 in the AChR-Ab+ population and in the MuSK-Ab+ population are similar to the definition of the primary endpoint except the population is based on the subjects in the FAS with the corresponding baseline antibody status only.

Similar to the primary endpoint as mentioned in Section 3.4.2.2, a supplementary analysis will be performed using a treatment-policy strategy to address both intercurrent events of rescue therapy and treatment discontinuation (i.e., including data collected after rescue therapy use and/or treatment discontinuation in the analysis).

The estimate of the treatment effect estimator will be based on a contrast from a MMRM model [REDACTED]

[REDACTED]

Changes from baseline in QMG at Week 26 in the AChR-Ab+ population and Changes from baseline in QMG at Week 26 in the MuSK-Ab+ population

The definitions of primary estimand of the changes from baseline in QMG at Week 26 in the AChR-Ab+ population and in the MuSK-Ab+ population are similar to the definition of the primary endpoint except the population is based on the subjects in the FAS with the corresponding baseline antibody status only.

[REDACTED]

The estimate of the treatment effect estimator will be based on a contrast from a MMRM model [REDACTED]

3.4.5 Other Secondary Efficacy Endpoints and Analyses

3.4.5.1 Other Secondary Efficacy Endpoints

The other secondary efficacy endpoints include:

- Proportion of subjects with both (1) ≥ 3 -point improvement in MG-ADL score at Week 26 and (2) no use of rescue therapy between Day 28 and Week 26 in the overall study population, AChR-Ab+ and MuSK-Ab+; and at Week 52 and no use of rescue therapy between Day 28 and Week 52 in AChR-Ab+ population.
- Change from baseline in MG-ADL score at Week 52 in the AChR-Ab+ population.
- Change from baseline in QMG score at Weeks 52 in the AChR-Ab+ population.
- Change from baseline in MGC score at Week 26 in the overall study population, AChR-Ab+ and MuSK-Ab+ and at Week 52 for AChR-Ab+ population.
- Change from baseline in revised MGQOL-15r score at Week 26 in the overall study population, AChR-Ab+ and MuSK-Ab+ and at Week 52 in AChR-Ab+ population.
- Patient Global Impression of Change score at Week 26 in the overall study population, AChR-Ab+ and MuSK-Ab+ and at Week 52 for AChR-Ab+ population.
- Time to first MG exacerbation by Week 26 in the overall study population, AChR-Ab+ and MuSK-Ab+ and by Week 52 in AChR-Ab+ populations
- The proportion of subjects with steroid tapered to ≤ 5 mg/day steroid at Week 26 for the overall study population, AChR-Ab+ and MuSK-Ab+ and by Week 52 for AChR-Ab+ population.
- The proportion of subjects in whom steroid dose was reduced by $\geq 50\%$ from baseline by Week 26 for the overall study population, AChR-Ab+ and MuSK-Ab+ and by Week 52 for AChR-Ab+ population.
- Proportion of subjects achieving minimal symptom expression, defined as MG-ADL= 0 or 1, at Week 26.

